# Analysis of Secondary Endpoint

### 8.8.2. Secondary Endpoint

The secondary objective of this study is to assess the participants' overall experience with Marathon® and CavilonTM. Results from the survey will be reported using the appropriate descriptive statistics for the distribution and scale of the data.

At Visit 1, participants will be asked the following question regarding the SBP on each arm:

1. Is the SBP comfortable? (Likert-like scale)

At Visit 3 and Visit 6, participants will be asked the following questions regarding the SBP on each arm:

Medline Industries, LP
An evaluation of the skin protection characteristics of two commercially available skin barrier protectants
MED-2022-DIV71-003
08-AUG-2022

Version 2.0 CONFIDENTIAL Page 24 of 28

- 1. Do you see the SBP on your skin? (Yes/No)
- 2. Did the SBP accumulate dirt or debris? (Yes/No)
- 3. Did the SBP adhere to clothing or any other material? (Yes/No)

Additionally, at Visits 3 and 6, participants will be asked the following questions regarding the SBP on each arm:

1. On which arm (left or right) is it easier to visually determine that the SBP is present?

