### 2.3. Risk/Benefit Profile

# 2.3.1.Potential Study Risks

This study entails minimum risk to the study participants. The SBPs used in the study are commercially available products that can be used in both home and clinical settings. There may be a minor risk of skin irritation for the participants. In such a case, for Marathon®, a clean tissue can be used before the film formed by the SBP dries. If the film has already dried, petroleum jelly can be used to soften the film, after which the SBP can be removed. In case of CavilonTM, the SBP can be removed using an adhesive remover containing hexamethyldisiloxane (HMDS). The risk to the study personnel is minimal, as they will use an applicator to apply the SBPs to the participants' volar forearms and inner elbows. The risk is further minimized as the study personnel will wear gloves during application of the SBPs.

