#### 6.5. Administration of Survey

Participants will complete surveys on Visits 1, 3, and 6, regarding their experience with the two SBPs.

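### Comfort is surveyed only at the application visit, so the survey cannot describe or compare comfort during wear

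*Combined protocol and SAP*

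**What the plan says.** Section 6.5 fixes the survey occasions: "Participants will complete surveys on Visits 1, 3, and 6, regarding their experience with the two SBPs". The Schedule of Activities (Section 1.2) gives the same three visits.

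Section 8.8.2 assigns the items. The Visit 1 set opens with "At Visit 1, participants will be asked the following question regarding the SBP on each arm" and contains one item, "Is the SBP comfortable? (Likert-like scale"). The later set opens with "At Visit 3 and Visit 6, participants will be asked the following questions regarding the SBP on each arm" and contains "Do you see the SBP on your skin? (Yes/No"), "Did the SBP accumulate dirt or debris? (Yes/No") and "Did the SBP adhere to clothing or any other material? (Yes/No"). A further item at those two visits asks on which arm the product is easier to see. Comfort is not in the later set. Survey results are to be reported with descriptive statistics.

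Section 3 words the secondary objective as collecting information on participants' experience with the two products. Section 8.8.2 restates it as their overall experience.

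On safety, Section 2.3.1 says "There may be a minor risk of skin irritation for the participants". The Schedule of Activities marks ADE monitoring at Visit 1, Visits 2 to 5 and Visit 6.

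**The concern.** The products are worn and followed for about a week, and the survey is the only secondary endpoint. Section 2.3.2 expects participant feedback to help inform clinical use decisions. With comfort asked only on the day of application, the only comfort result the report can give is a first-day one. A film that begins to itch, pull or feel tight on Day 3 would score the same as one that does not.

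A reader who sees comfort results from a seven-day study may take them to describe the seven days. The data would not support that, and the survey could not show a difference between the products that appears only with wear.

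**Working it through.** The point rests on which items are asked at which visits. The plan states no figure for it to reproduce; 42 completers is taken from Sections 5.3 and 5.4 for counting only.

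**1. Items by visit (Sections 6.5 and 8.8.2; ADE row from Section 1.2)**

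| Item | Visit 1 | Visit 3 | Visit 6 |
|---|---|---|---|
| Comfort, each arm | yes | no | no |
| Film visible, each arm | no | yes | yes |
| Dirt or debris, each arm | no | yes | yes |
| Sticks to clothing or other material, each arm | no | yes | yes |
| Arm on which film is easier to see | no | yes | yes |
| ADE monitoring | yes | yes | yes |

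Comfort is asked at 1 of 3 survey visits and at 0 of the 2 that follow a period of wear.

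**2. Timing of the three surveys**

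- Visit 1 is the application visit. The Schedule of Activities lists the survey after application, drying and the post-application reading. Section 6.2.3 lets drying be as short as one minute. That the rating is given soon after application is inferred from this order; no survey time within the visit is stated.
- Visit 3 follows two intervals of 24 ± 4 hours (Sections 6.2.3 and 6.3.1): 2 × 24 = 48 hours, with limits 2 × 20 = 40 and 2 × 28 = 56 hours. All of this lies inside the first 72 hours, which Section 4.1 calls the more important window for wear time.
- Visit 6 falls on Day 8 (Section 8.8.1): 7 × 24 = 168 hours, approximately. A Monday start gives Visit 6 on the next Monday, and a Tuesday start on the next Tuesday.

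**3. Counts**

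- Comfort ratings planned: 42 × 2 arms × 1 visit = 84.
- Ratings possible at existing later surveys but not collected: 42 × 2 arms × 2 visits = 168, of which 84 at Visit 3 and 84 at Visit 6.

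**4. Does ADE monitoring fill the gap?**

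It runs at all six visits, and Grade 1 in Section 7.4 includes mild symptoms, so irritation has a route into the record. It does not replace a comfort rating, for four reasons:

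- Section 7.1 defines an ADE as an event related to the device and arising from inadequate instructions, deployment, operation, malfunction or use error. Mild tightness or itch under a correctly applied film may not meet that definition.
- The plan describes no comfort scale per arm within ADE monitoring.
- Study personnel apply the products and record the ADEs (Sections 6.2.3 and 7.7). Only the participants are described as blinded (Section 8.2), so a participant's own rating is the blinded measure.
- Section 8.3 plans no safety analysis group, and Section 8.8 plans no ADE summary by product.

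**The case against.** The strongest reply is that discomfort does have a route into the data. ADEs are monitored at every visit, mild symptoms count as Grade 1, and changes in severity and intermittent episodes are documented (Section 7.7). The principal investigator reviews all ADEs (Section 9.1.2). This stands against the reading, which a reader might infer, that discomfort after Visit 1 goes wholly unrecorded. It does not supply a blinded comfort rating for each arm, and discomfort below the ADE threshold can still be missed.

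Second, the plan sets no objective on tolerability. The objective is participant experience, the endpoint is simply the survey responses, and three aspects of experience during wear are asked at Visits 3 and 6. This also stands: the survey should not be said to fail a tolerability aim. Comfort is nevertheless part of overall experience, and the plan itself treats it so by asking about it at Visit 1.

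Third, both products are expected to wear off (Sections 2.2.1 and 2.2.2), so by Day 8 a comfort question may have nothing to refer to on some arms, and a change from Visit 1 could mix comfort with loss of film. This is a fair limit on a Visit 6 rating and shapes the fix. It has less force at Visit 3.

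Finally, the 168 uncollected ratings are a count. They do not measure bias, and some of the Visit 6 ratings might not be interpretable.

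**Conclusion.** The point holds in a limited form. The survey does not measure comfort after Visit 1, so it cannot describe or compare comfort during wear, and later discomfort is recorded only if it is identified as an ADE. The gap is 2 of 3 survey visits, or 168 possible ratings with 42 completers.

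This affects one part of a descriptive secondary endpoint. The primary endpoint, its tests and the sample size do not depend on it. The conclusion assumes that the items listed in Section 8.8.2 are the full survey and that the Visit 1 survey follows application, as the order of the Schedule of Activities suggests. It does not depend on how many minutes after application the question is asked.

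**What to change.** In Section 8.8.2, add the existing comfort item, on the same Likert-like scale and for each arm, to the Visit 3 and Visit 6 surveys. Either add a response option for film that is no longer present or cannot be felt, or state that comfort will be interpreted alongside the existing item on whether the film can be seen.

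Report comfort descriptively by product at each of the three visits. Name Visit 3 as the main time point during wear, because it lies within the 72-hour window that the protocol calls more important. Describe the Visit 1 result as comfort on the day of application.

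The cost is a small revision of the survey and case report form, notice to the IRB, and a few seconds per participant at two existing visits. It needs no extra visit, no change in sample size and no change to how ADEs are identified or handled.

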### 5.4 Early Withdrawal and Replacement

Participants will be discontinued or withdrawn from study participation at any time if either the participants or the study personnel feel that it is not in the participants' best interest to continue participation.

Participation in the study may end at several critical points:

Medline Industries, LP
An evaluation of the skin protection characteristics of two commercially available skin barrier protectants
MED-2022-DIV71-003
08-AUG-2022

Version 2.0 CONFIDENTIAL Page 15 of 28

- Participant withdraws from the study for any reason.
- Participant is not compliant with study procedures.
- Participant presents with adverse event(s) such that in the opinion of the PI it is in the best interest of the participant to discontinue study participation.
- Protocol violation requiring discontinuation of use of the study product(s).

Based on the above reasons, if any participant withdraws from the study or is dismissed, another participant will be recruited such that the total number of participants who complete the study will be 42. If a participant is being replaced, the randomization sequence associated with the replaced participant will be used for the new participant.

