### 8.3. Populations for Analyses

The analyses will be performed on the intent to treat (ITT) population which consists of all participants who have complete data for all time points and have completed the survey for the secondary endpoint.

No per protocol, safety, or other analyses groups are planned.

Medline Industries, LP
An evaluation of the skin protection characteristics of two commercially available skin barrier protectants
MED-2022-DIV71-003
08-AUG-2022

Version 2.0 CONFIDENTIAL Page 22 of 28

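### Section 8.3 drops Visit 1 comfort ratings already collected from participants who are later withdrawn, so the comfort summary describes completers only (minor)

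*Combined protocol and SAP*

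**What the plan says.** Section 6.5 sets the survey schedule: "Participants will complete surveys on Visits 1, 3, and 6". Section 8.8.2 lists the items. At Visit 1 there is one, asked for each arm: "Is the SBP comfortable? (Likert-like scale"). The items at Visits 3 and 6 cover visibility, dirt, sticking to clothing, and the arm on which the film is easier to see. Comfort is not repeated. The analysis is descriptive: "Results from the survey will be reported using the appropriate descriptive statistics for the distribution and scale of the data".

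Section 8.3 defines the analysis population, which it labels intent to treat, as "all participants who have complete data for all time points and have completed the survey for the secondary endpoint". It adds: "No per protocol, safety, or other analyses groups are planned".

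Section 2.3.1 names the foreseen harm, "There may be a minor risk of skin irritation for the participants", and explains how a film is taken off. For the sponsor's product once dry, "petroleum jelly can be used to soften the film, after which the SBP can be removed". Section 5.4 lists among the reasons for ending participation: "Participant presents with adverse event(s) such that in the opinion of the PI" considers stopping to be in that person's interest. Sections 5.3, 5.4 and 8.2 replace anyone who leaves or has incomplete data, until 42 have complete data.

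**The concern.** A comfort rating needs only Visit 1. Under 8.3, whether it is counted depends on what happens at Visits 2 to 6, and one thing that can happen is withdrawal for irritation caused by a study product. Inclusion of an early answer then depends on a later, possibly product-related event. Because each leaver is replaced, the analysis set contains nobody withdrawn for irritation, whatever the true rate.

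The secondary objective is participants' experience with the two products, and comfort is the survey's only tolerability item. Freedom from stinging is part of one product's name (2.2.1) and of the other's description (2.2.2), so readers will look at this result. The intent-to-treat label would also lead them to expect that everyone treated is included.

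**Working it through.** **1. Is the rating really lost?** Take a participant who receives both products and rates both arms at Visit 1, then is withdrawn at Visit 3 for irritation.

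- 8.8.2: the rating exists and is complete.
- 8.3: the participant lacks later time points, so is outside the only analysis set.
- 5.4 and 8.2: a replacement takes over the randomization sequence and the count returns to 42.
- 8.7: missing data are to be quantified and possible bias discussed. The Visit 1 rating is not missing, and no rule returns it to the table.
- 8.8: summaries are for the full sample with non-missing counts, but 8.3 defines the sample.

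The rating was collected and is left out.

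**2. The plan's own figure.** There is none for comfort. The 42 used below comes from 8.1: a paired t-test on 17.5 − 15 = 2.5 with SD 5.05 and α = .0125 one-sided gives n = 42 (power 0.807). The point does not depend on it.

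**3. How large could the effect be?** Let k be the number of leavers who answered at Visit 1, m the completers' mean for a product and s the leavers' mean.

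Planned mean = m. All-treated mean = (42m + ks)/(42 + k). Overstatement = k(m − s)/(42 + k).

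This is zero when k = 0 or s = m, positive when s < m, and negative when s > m. If leavers rate the other product at its completers' mean, the contrast between products shifts by the same amount.

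The documents give no k, m, s or scale length. Assuming a 5-point scale and m = 4:

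| k | share of ratings dropped, k/(42+k) | s = 3 | s = 2 | s = 1 |
|---|---|---|---|---|
| 1 | 2.3% | 0.02 | 0.05 | 0.07 |
| 2 | 4.5% | 0.05 | 0.09 | 0.14 |
| 3 | 6.7% | 0.07 | 0.13 | 0.20 |

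Example: k = 3, s = 1 gives 3 × 3/45 = 0.20.

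**4. Extreme case for a proportion.** Suppose no completer and every leaver calls a product uncomfortable. Exact (Clopper-Pearson) 95% intervals:

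| | uncomfortable | 95% CI |
|---|---|---|
| As planned | 0/42 = 0% | 0 to 8.4% |
| k = 1 | 1/43 = 2.3% | 0.1 to 12.3% |
| k = 2 | 2/44 = 4.5% | 0.6 to 15.5% |
| k = 3 | 3/45 = 6.7% | 1.4 to 18.3% |

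The intervals overlap heavily. What changes is the description, from nobody to somebody.

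**5. Chance that it arises at all.** If each participant has risk p of leaving for irritation, the chance of at least one among the first 42 treated is 1 − (1 − p)^42. For assumed p of 0.5%, 1% and 2% this is 19%, 34% and 57%.

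**The case against.** The strongest reply is that the chain is long. Irritation must occur, must lead to withdrawal rather than only removal of the film, must do so after the Visit 1 survey, and must already show in a rating given on the day of application. Section 2.3.1 calls the risk minor, and 5.2 excludes self-reported allergy or sensitivity to either product. A leaver whose irritation began later may have rated the product just as completers did, and then nothing is biased. The endpoint has no test or decision rule. All of this stands, and it is why the point is minor.

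A second reply is that nothing is hidden. Adverse device events are monitored at each visit from Visit 1 (1.2), recorded with severity (7.7) and reviewed by the investigator (9.1.2), and 8.7 should bring the leavers' missing later data into the report. This is largely right. A reader might infer that irritation disappears from the record, and the documents do not support that. What is lost is the leaver's place in the comfort summary. Section 8 also names no tabulation of these events by product.

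A third reply is that the repeated Corneometer readings call for complete cases. Whatever the merit of that for the primary endpoint, a descriptive item asked once does not need data through Visit 6.

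**Conclusion.** The point holds as a minor one. The text of 8.3, read with replacement of leavers, excludes collected Visit 1 comfort ratings because of later events that a product can cause, and no other section restores them. The direction is conditional: comfort is overstated only if leavers rated a product worse than completers did. The size cannot be derived from the documents. The figures above rest on assumed scale length, scores and withdrawal risks, and suggest a small shift in the mean.

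Two stronger readings are tempting and not supported. One is that the comfort comparison is materially biased towards one product: no document gives an irritation or withdrawal rate for either, so neither the existence nor the direction of a bias is established. The other is that readings taken after a film is removed are mishandled in participants who stay. Sections 6.3.1 and 8.8.1 have those readings taken and analysed as observed, which fits an endpoint that measures loss of the film.

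**What to change.** - **8.3:** state that survey items are summarised by product for every participant who received an SBP and answered the item, including those later withdrawn or replaced, with the number answering shown per visit.
- **8.8.2:** report skin-irritation adverse device events, and withdrawals for irritation, by product out of all participants treated, including those replaced.

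The cost is two sentences and one small table. The Visit 1 answers and the events are already collected. The only downside is that survey tables carry their own denominators, up to 42 + k at Visit 1 for k leavers who answered. The Corneometer analysis set, tests, sample size, replacement rule and participant blinding need not change. If nobody who answered is later excluded, the comfort summary is the same as now planned.

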## 2.2.2 3MTM CavilonTM Advanced Skin Protectant (referred to as CavilonTM)

CavilonTM (#MMM5050CS) is a polymeric-cyanoacrylate solution intended for the protection of intact or damaged skin. It is effective in conditions where skin is exposed to moisture and caustic irritants such as feces, digestive fluids, wound drainage and urine, frequently or continuously. It can also be used in areas exposed to friction and shear from bedding, clothing, shoes or any other material that would rub against the skin. Upon application to skin, the liquid dries rapidly to form a primary long-lasting waterproof, highly durable film barrier. It is elastomeric, adhering to the contours of the skin and providing a uniform film. The film is transparent and possesses good oxygen and moisture vapor permeability. The polymer-cyanoacrylate is dispersed in a non-stinging solvent. The film is colorless, non-cytotoxic and has a low dermatitis potential. The film adheres to dry, moist or wet skin surfaces and remains intact during conditions of continuous or repeated exposure to moisture or caustic irritants. It will wear off the skin and does not require removal.

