### 8.8. Statistical Analysis

Statistical analyses will be conducted in SAS® software, Version 9.4 or higher of the SAS System for Windows (Copyright © 2013 SAS Institute Inc.) or other appropriate statistical software. P < .05 will be considered statistically significant.

All continuous variables will be summarized for the full sample and by SBP group using the following descriptive statistics: (non-missing sample size), mean, standard deviation, median, maximum and minimum. The frequency and percentages (based on the non-missing sample size)

Medline Industries, LP
An evaluation of the skin protection characteristics of two commercially available skin barrier protectants
MED-2022-DIV71-003
08-AUG-2022

Version 2.0 CONFIDENTIAL Page 23 of 28

of observed levels will be reported for all categorical measures. 95% confidence intervals will be calculated for all means.

Spearman correlation analysis will be used to examine possible associations between the key variables of Marathon® or Cavilon™ use and the Corneometer® measurements at various timepoints with covariates of age, sex, and dominant arm. Additional t-tests or non-parametric tests will be employed to further examine any significant associations found in the correlational analyses between key and covariate measures.

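### A 'No' on the dirt and clothing-adherence items can mean clean film or film already gone, which tends to favour the product that wears off sooner

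*Combined protocol and SAP*

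**What the plan says.** Section 8.8.2 introduces three items per arm with "At Visit 3 and Visit 6, participants will be asked the following questions regarding the SBP on each arm". They are, in order, "Do you see the SBP on your skin? (Yes/No"), "Did the SBP accumulate dirt or debris? (Yes/No") and "Did the SBP adhere to clothing or any other material? (Yes/No"). No response for film that is no longer there is listed, and no recall period is given.

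On analysis, the same section says "Results from the survey will be reported using the appropriate descriptive statistics for the distribution and scale of the data". Section 8.8 sets the general rule for categorical measures: "The frequency and percentages (based on the non-missing sample size") of the observed levels. Section 8.3 limits the analysis set to participants who, besides having complete data, "have completed the survey for the secondary endpoint". A blank is therefore unlikely to serve as an informal 'not applicable'.

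Both films are expected to disappear. Section 2.2.1 says that Marathon wears off as skin regenerates, and section 2.2.2 says of Cavilon "It will wear off the skin and does not require removal". Section 3 makes the comparison of wear and durability the primary objective.

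**The concern.** Film that has gone cannot collect dirt or catch on clothing, and film lost early had less time to do either. A participant whose film has gone can only answer 'Yes' or 'No', and 'No' reads as a good result. The plan does not say that items 2 and 3 will be read together with item 1 or with the Corneometer reading taken at the same visit, although both are available.

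The products are being compared precisely because they may differ in wear. If they do, part of any difference in the 'Yes' percentages for dirt and adherence may reflect wear rather than cleanliness or stickiness of the film. Shorter wear could then be read as a better participant experience. Survey responses are the only secondary endpoint, and section 2.3.2 (potential benefits) expects participant feedback to help inform clinical use.

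**Working it through.** **The plan's own figures.** The plan states no figure for the survey items. Its one recomputable figure is N = 42. A paired t-test for superiority by a margin, with standardised distance (17.5 − 15)/5.05 = 0.495 and one-sided alpha 0.0125, gives n = 42 (power 0.807). The figure reproduces but does not bear on this point.

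**Inputs.** From the documents: Yes/No responses, all non-missing answers as denominator, and one arm per product in each of 42 participants. Assumed, because the documents give no values:
- *q*: share of a product's arms with film still present at the visit
- *p*: chance of 'Yes' when film is present
- *r*: chance that lost film is still answered 'Yes', relative to *p*

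**Formula.** P(Yes) = q·p + (1 − q)·r·p. With the same *p* and *r* for both products, the gap is (q₁ − q₂)·p·(1 − r).

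**No recall of lost film (r = 0), same p for both products**

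| Film present | p = 20% | p = 40% | p = 60% |
|---|---|---|---|
| equal | 0 points | 0 points | 0 points |
| 90% vs 70% | 4 | 8 | 12 |
| 90% vs 50% | 8 | 16 | 24 |
| 90% vs 30% | 12 | 24 | 36 |

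**Dependence on recall (p = 40%, presence 90% vs 30%)**
- r = 0: 0.90 × 0.40 = 36% vs 0.30 × 0.40 = 12%, about 15 vs 5 of 42.
- r = 0.5: 36% + 0.10 × 0.5 × 40% = 38% vs 12% + 0.70 × 0.5 × 40% = 26%.
- r = 1: 40% vs 40%.

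**The ranking can reverse.** Take r = 0, true rates while film is present of 30% vs 50%, and presence of 90% vs 40%. The summary shows 0.30 × 0.90 = 27% vs 0.50 × 0.40 = 20%, so the product with the worse film looks better.

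**Accurate recall may not mean r = 1.** Exposure time also counts. With an assumed constant daily risk of 5%, film worn 7 days has 1 − 0.95⁷ = 30% and film worn 3 days has 1 − 0.95³ = 14%, even if every problem is remembered.

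**What splitting the 'No' answers would show** (p = 40%, presence 90% vs 30%, r = 0, presence classified without error)

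| Category | Product 1 | Product 2 |
|---|---|---|
| Problem reported | 36% | 12% |
| No problem, film present | 0.90 × 0.60 = 54% | 0.30 × 0.60 = 18% |
| No problem, film gone | 10% | 70% |

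The last row explains the low 'Yes' percentage of product 2. The planned summary would not show it.

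**The case against.** **The all-participant percentage is a legitimate quantity.** The secondary objective concerns participant experience, and film that has gone and no longer bothers the wearer is part of that. This stands. The overall percentage should stay, and the difficulty arises only when it is read as a property of the film.

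**Both items are in the past tense.** Participants may report a problem with film since lost. This also stands: recall shrinks the gap, and r = 1 removes it. The documents do not fix *r*, because no recall period is stated.

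**Silence is not exclusion.** The general wording on descriptive statistics does not forbid a cross-tabulation, and the Corneometer results will be reported by product and visit anyway. The survey form is a separate document and could contain another response option. These points are fair, but nothing in the plan commits to reading the items together, and group-level wear results do not show which 'No' answers came from bare skin.

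**Stronger readings to avoid.** A reader might infer from the emphasis on the first 72 hours that much film is gone by Day 8. That remark only justifies the daily readings; it says nothing about film remaining at Visit 6, and section 2.2.2 describes Cavilon as long-lasting. Nor do the documents give reason to expect substantial differential loss at Visit 3, about 48 hours after application. A reader might also conclude that the secondary endpoint as a whole is biased. The argument does not extend to the comfort or visibility items.

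**Presence is hard to classify.** Item 1 asks whether film is seen. Both films are transparent, section 8.5 expects skin phototype to matter for seeing them, and dirt may itself make film visible. Each arm has two treated sites but gets one answer. This stands and limits what any split table can show.

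**Conclusion.** The point holds for items 2 and 3 only, as an expected tendency of unknown size. As planned, a 'No' does not distinguish clean film from film that has gone or was worn for less time, and the direction favours the shorter-wearing product if wear differs. In the assumed scenarios with the same film-specific rate, the artificial gap runs from zero (equal presence or r = 1) to 36 points (90% vs 30% presence, 60% rate, no recall). None of these inputs comes from the documents, so the figures show what is possible and do not estimate what will occur. The items are descriptive, with no planned test, so the consequence is for interpretation and product statements. This is a worthwhile, inexpensive improvement rather than a flaw that threatens the trial.

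**What to change.** In section 8.8.2:

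1. Keep the all-participant percentages. For items 2 and 3, add a table for each product and visit with three categories: problem reported; no problem and film seen (item 1 'Yes'); no problem and film not seen (item 1 'No').
2. Add a sensitivity version that takes presence from the same-visit Corneometer readings of that arm's two test areas, set against its post-application and untreated-control readings. Fix the rule for calling film present on an arm before analysis.
3. Label the table descriptive, because film presence is a post-randomisation outcome. Read it as shares of all analysed arms. The first category can include problems recalled from film since lost, so dividing it by the first two categories does not give a rate among arms with film.
4. Do not state that one product is cleaner or less adherent from the Visit 6 'Yes' percentage alone.
5. State one recall period for both items. Wording limited to the time since the last survey would not solve the problem: at Visit 6, film lost before Visit 3 could then only be answered 'No'.

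The cost is one cross-tabulation of data already collected, one pre-specified presence rule and a short phrase in two survey items. No visits or participants are added. The downside is that item 1 measures visibility of a transparent film, so presence will be imperfectly classified, possibly differently by product.
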